# 17.4.4. Secondary Outcome 3: Change over time from baseline measures

This outcome will assess if there is evidence of a difference between arms in the change over time from baseline to the end of MV for the following measures:

- Ventilation Index (VI)
- Oxygenation Index (OI)
- Oxygenation Saturation Index (OSI)
- SpO2/FiO2 (SF) ratio

VI, OI and OSI will be measured by taking capillary blood gas sampling immediately prior to intervention and then at 6, 12, 24, 36 and 48hrs while still on MV and will continue every 48hrs if still on MV.

SF ratio will be reported at the above times while on MV but will also continue post MV and will be recorded every time peripheral O2 measurement is recorded in routine notes and at least twice in a 24-hour period.

# Form prepared: 16/04/2024 v2.0 for BESS Page 17 of 30

# 17.4.4.1. Derivation

The required blood gas readings to calculate VI, OI, OSI and SF can be found on the Observations and Outcomes CRF. The following table lists all the required variables.

Blood gas reading	Description	MACRO
		variable name
MAP **	Mean airway pressure	OAOMAPI
PIP **	Peak Inspiratory Pressure	OAOPIPI
PEEP **	Positive End Expiratory Pressure	OAOPEEPI
RR	Respiratory rate	OAORSPRI
PaCO 2 *	Partial pressure of arterial carbon dioxide	OPOPACMC
FiO 2	Fraction of air inspired that is oxygen	OAOFIO2I
PaO 2 *	partial pressure of arterial of oxygen	OAOPAO2I
SpO 2	peripheral oxygen saturation	OAOSPO2I
рН	Hydrogen ion concentration (acidity or alkalinity)	OAOPHRR

The following formulas will be required to calculate the blood gas indices:

- VI = (PaCO2 × (PIP-PEEP) × RR)/1,000
- $OI = (MAP \times FiO_2 \times 100)/PaO_2$
- OSI = (MAP × FiO2 × 100)/SpO2
- SF = SpO2/FiO2

\**Note:* PaCO2 and PaO2 can be recorded in units of either mmHg or kPa. To conduct the analysis all measurements in kPa will be converted to mmHg using the following formula [6]

1 mmHg = 0.133 kPa Example conversion: 30 kPa = 30 / 0.133 = 225.6 mmHg

\*\***Note:** MAP, PIP and PEEP can be recorded in units of either cmH2O or mbar. To conduct the analysis all measurements in cmH2O will be converted to mbar using the following formula [6]:

# $1 \ cmH_2O = 0.981 \ mbar$ Example conversion: $5 \ cmH_2O = 5 \ x \ 0.981 = 4.903 \ mbar$

Effective Shunt is an estimate of the proportion of cardiac output that would have to bypass the lungs entirely to obtain these blood gas results at a steady state. The predictive validity of ES in critically ill adults has been reported but this has not yet been explored as a useful indicator in the paediatric population.

#### 17.4.4.2. Analysis

Summary statistics will be presented in a table for each time point (0 hours, 12, hours, 24 hours, 36 hours, 48 hours then every 24 hours while still on MV if the number of observations is  $\geq$  5 overall at the time points following 48 hours) detailing the mean and standard deviation of each of the derived measures (VI, OI and OSI) for each treatment arm and overall.

The relationship between longitudinal data for VI, OI and OSI and the event of successful extubation will be examined visually by plotting mean profile plots of longitudinal data separated by treatment group and by the time at which the final observation was observed and comparing this to the overall mean profile plot separated by treatment group.

Infants will have differing amounts of follow-up data for the outcomes VI, OI and OSI as these are recorded while on MV only. More specifically, infants who are successfully extubated earlier (and therefore completing follow-up earlier) will have less follow-up data than infants with a later successful extubation time. This will be addressed in analyses of both the longitudinal measurements (VI, OI and OSI) and the time to event outcome (time to successful extubation) using joint modelling. Joint modelling will account for the potentially informative drop-out in longitudinal measures due to successful extubation. For each measure the treatment effect will be reported together with a 95% CI and a p-value.

For the SF ratio, a repeated measures random effects model will be fitted. The dependent variable will be post baseline (0 hours) SF ratio measurements. Covariates will be: SF ratio at baseline (0 hours), treatment arm, time (fitted as a continuous variable), and the stratification factor of time on ventilation prior to randomisation (<24h and  $\geq$ 24h). Centre will be fitted as a random intercept. The treatment effect (estimated mean difference in SF ratio) will be reported together with a 95% CI and a p-value.

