11.3 Sample Size calculation

The study will be powered to detect a minimally clinically important difference of 18 hours (0.75 days) in the primary outcome variable of time of mechanical ventilation. Data are expected to be positively skewed, and will therefore be log-transformed, and resulting data back-transformed. The null hypothesis is that of no difference in time of MV between the two groups.

Data from Alder Hey Children's Hospital from an audit of 60 eligible infants admitted to PICU in the seasons 2012/3 and 2013/4 showed a mean (SD) duration of ventilation of 4.83 (2.5) days (PICANet data, 2011-14). Parameters for sample size estimation are therefore as follows:

```
E(Y_1) = 4.83 \text{ and } SD(Y_1) = 2.5 E(Y_2) = 4.08 \text{ and } SD(Y_2) = 2.5 \delta = E(Y_2)/E(Y_1) = 0.845 giving coefficients of variation: \kappa_1 = SD(Y_1)/E(Y_1) = 2.5/4.83 = 0.518 \kappa_2 = SD(Y_2)/E(Y_2) = 2.5/4.08 = 0.613
```

Using the formula of Wolfe and Carlin (1999) with r = 1 for equal allocation and a two-sided alphalevel of 0.05, sample size estimations are 100 per group for 80% power and 134 per group for 90% power.

Taking the sample size of 134 and allowing for 5% dropout requires 142 patients will be recruited to each group, giving a total of 284 participants overall.

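### The SAP names no baseline, stratum or site term, and no reported coefficient, for the VI, OI and OSI joint models, so their treatment effects may be imprecise or diluted

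*SAP*

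**What the plan says.** SAP 17.4.4 sets the target for VI, OI, OSI and the SF ratio as the "difference between arms in the change over time from baseline to the end of MV". Readings are scheduled before the first dose and at 6, 12, 24, 36 and 48 h, then continue while the infant is ventilated.

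For VI, OI and OSI, SAP 17.4.4.2 explains that infants extubated early have fewer readings, and that joint modelling of the index and time to successful extubation will deal with this. On the estimate it says only: "For each measure the treatment effect will be reported together with a 95% CI and a p-value". It does not give the covariates, the role of the 0 h value, or the submodel and term that supply the effect.

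The next paragraph specifies the SF model. The response is post-baseline SF. The covariates are "SF ratio at baseline (0 hours), treatment arm, time (fitted as a continuous variable") and the prior-ventilation stratum. Centre is a random intercept, and the effect is defined as a mean difference.

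Protocol 11.5 names joint modelling for these outcomes and lists no covariates.

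**The concern.** An outcome defined as change from baseline needs a stated role for baseline, and here there is none. The gap is also out of line with the rest of the SAP. The primary mixed model (17.4.1.2), the SF model (17.4.4.2), the LRSQ model (17.4.9.2) and the Cox model (section 19) all list prior ventilation. The Cox model does so for the same extubation event that forms the event part of the joint models.

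These indices are the trial's physiological evidence on gas exchange. Each will carry a p-value, with no multiplicity adjustment (SAP 12). Independent programming covers only the primary and safety analyses (SAP 21). One data set could therefore give noticeably different estimates or interval widths depending on a choice that is not written down and that no planned second programming would reveal.

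**Working it through.** **The plan's own figures.** The documents give no SD, correlation, effect size or power for VI, OI or OSI. The only sample size is for the primary outcome (Protocol 11.3). I reproduced it because the simulation below borrows its inputs.

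- Inputs: "showed a mean (SD) duration of ventilation of 4.83 (2.5) days" and a target mean of 4.08 days.
- Log-scale variances: ln(1 + (2.5/4.83)²) = 0.2374 and ln(1 + (2.5/4.08)²) = 0.3188.
- Log-scale difference: ln(4.08/4.83) − 0.5 × (0.3188 − 0.2374) = −0.2095.
- n per group at 90% power: (1.960 + 1.2816)² × 0.5562 / 0.2095² = 133.2, so 134. At 80% power: 99.5, so 100.
- With dropout: 134/0.95 gives 142 per group and 284 in total. All match the protocol.

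**Closed form.** Assume equal correlation ρ between any two readings, unit variance, m post-dose readings and a constant effect after dosing.

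- Variance of the post-dose mean, unadjusted: (1 + (m − 1)ρ)/m. Adjusted for baseline: the same minus ρ².
- With the 0 h value as a response under a constant treatment term, the effect is multiplied by m/(m + 1).

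At the five post-dose readings scheduled by 48 h:

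| ρ (assumed) | Unadjusted variance | Adjusted variance | CI width ratio |
|---|---|---|---|
| 0.3 | 0.44 | 0.35 | 1.12 |
| 0.5 | 0.60 | 0.35 | 1.31 |
| 0.7 | 0.76 | 0.27 | 1.68 |

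Dilution is 1/(m + 1): 17% at five readings, 25% at three and 33% at two.

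**Simulation of the longitudinal part.** I ran 150 trials at each ρ, with 268 infants (2 × 134) and log-normal ventilation times from the mean and SD above. Readings were at 0, 6, 12, 24, 36 and 48 h, then daily, which gave about 7.3 post-dose readings per infant. Further assumptions were a true effect of −0.5 SD from the first post-dose reading, a stratum effect of 0.3 SD in 40% of infants, and dropout unrelated to the index.

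| Specification | Estimate (true −0.50) | SE at ρ = 0.3 / 0.5 / 0.7 |
|---|---|---|
| Post-dose values, baseline and stratum as covariates (SF form without centre) | −0.50 | 0.074 / 0.070 / 0.064 |
| Post-dose values, no covariates | −0.50 | 0.084 / 0.089 / 0.107 |
| 0 h as a response, constant treatment term | −0.44 | 0.081 / 0.088 / 0.106 |
| 0 h as a response, treatment acting only after baseline | −0.50 | 0.074 / 0.069 / 0.064 |

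- Second row against first: 0.084/0.074 = 1.14, 0.089/0.070 = 1.27, 0.107/0.064 = 1.67. With 150 runs, each SE carries about 6% Monte Carlo error (1/√(2 × 149)).
- Third row: 1 − 0.436/0.50 = 13% dilution.
- A fifth option keeps 0 h as a response and reports a treatment-by-time slope. When the true effect grows linearly (−0.15 per day) it returns −0.15, with no dilution. When the true effect is the −0.5 step, the slope is only about −0.03 per day.

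The schedule after 48 h is itself inconsistent: SAP 17.4.4 has readings every 48 h, while SAP 17.4.4.2 and the protocol have them daily. Fewer readings move the dilution from 13% towards 17%.

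**The case against.** The strongest reply is that silence is not an unadjusted model. A reader might infer that the reported effects will be diluted or imprecise. The documents do not support that, because they state neither the response rows nor the reported term. Two specifications compatible with the text show no dilution: a treatment-by-time slope under a linear effect, and 0 h as a response with treatment acting only after dosing. The second is as precise as the adjusted model. This stands, and the consequence can only be put as possible. The slope is a weaker defence if the effect is a step, and Protocol 7.4 expects gas exchange to improve quickly after surfactant.

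A reader might also infer that chance imbalance at baseline would bias the unadjusted result. It would not: under randomisation the post-dose estimate is unbiased, and its interval already reflects chance imbalance. What is lost is precision. Nor can a power gain be quoted, since the documents give no effect size or SD for these indices.

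Third, Protocol 11.5 asks for the stratification factors in the primary analysis only, and the SAP uses plain t-tests for several secondary durations. Differing from the SF model is therefore not an error in itself. That is fair, but those t-tests are stated openly, whereas the joint model is left undefined for an outcome that refers to baseline.

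Finally, SF already has a baseline-adjusted model and is closely related to OSI: by the SAP's formulas, OSI = 100 × MAP/SF. That limits the importance of the point but does not define the other three analyses.

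**Conclusion.** The point holds as a gap in specification with a possible cost. Followed literally, 17.4.4.2 gives joint models with no covariates. On post-dose values alone the effect is unbiased, with an interval about 1.14 to 1.67 times as wide as the adjusted one. With the 0 h value as a response under a constant treatment term, the effect is diluted by about 13–17% with five or more post-dose readings, rising to 25–33% with three or two.

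These sizes rest on assumed correlations of 0.3 to 0.7, equal correlation between readings, and dropout unrelated to the index. They therefore isolate the covariate question and leave out the informative dropout that joint modelling is meant to handle. The outcomes are secondary, so the primary analysis and the sample size of 284 are unaffected.

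**What to change.** In SAP 17.4.4.2, for each of VI, OI and OSI:

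- Adjust the longitudinal submodel for the baseline value of that index. Either use it as a covariate with post-baseline responses, as for SF, or keep 0 h as a response with treatment acting only after baseline. The second form also keeps infants who have no later reading.
- Include the prior-ventilation stratum in both the longitudinal and the event submodel, as the section 19 Cox model already does for the same event.
- Handle site as for SF where the software allows.
- Name the submodel and coefficient reported as the treatment effect.

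Infants with no baseline value fall under the existing rule against imputation in SAP 17.1; no mean baseline should be carried in for them.

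The cost is a few sentences and extra terms in the planned joineR analysis, using data already scheduled for collection. The only downside is a small loss of infants under the covariate form. The wording should be settled before the randomisation codes are released to the statistical team.

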8.4 Procedures for assessing Efficacy

8.4.1 Efficacy Assessment 1

Efficacy will be assessed by group-wise comparison of the primary outcome measure group "Duration of MV after randomisation" by intention to treat. This is defined as time from randomisation to final extubation in hours, including any time off MV where the infant requires reintubation for a further period of MV. Time of randomisation and intervention will be recorded in the patients' notes and CRFs. MV ceases at extubation, an event when the endotracheal tube (breathing tube) is removed and the infant is allowed to breathe without invasive mechanical support. Extubation is an important discrete event in a patient's care pathway, is routinely recorded in the notes and PICANet audit.

8.4.2 Efficacy Assessment 2

The Ventilation Index (VI), Oxygenation Index (OI), Oxygenation Saturation Index (OSI) and SF ratio are secondary outcomes of efficacy derived from blood gas results (capillary blood gas sampling times as per Table 2 Schedule for intervention and follow-up), ventilator settings, and non-invasive monitoring. These data are captured through existing intensive care automated monitoring process or regular manual entry on large format (broad-sheet) bed-charts. This data will be transcribed by the research nurse to the CRF.

Mechanical Ventilation parameters to allow calculation of VI, OI, OSI and SF ratio must be recorded at the corresponding time when Blood Gas samples are scheduled to be taken for research or taken for routine purposes.

Mechanical Ventilation parameters are recorded regularly for ventilated patients as part of standard care. BESS does not require site teams to take any additional readings of these parameters for study purposes, but **all blood gas and ventilator readings** taken as part of standard care must be transcribed into the CRF to allow for calculation of these ratios over time.

After extubation, all inhaled Oxygen and peripheral oxygen saturation parameters recorded as part of standard care must be transcribed into the CRF to allow for calculation of this ratio over time. Blood gas indices and ratio definitions are as follows:

- VI = (PaCO₂ × (PIP-PEEP) × respiratory rate)/1,000
- OI = $(MAP \times FiO_2 \times 100)/PaO_2$
- OSI = $(MAP \times FiO_2 \times 100)/SpO_2$
- SF = SpO₂/FiO₂

MAP = mean airway pressure

PaCO₂ = partial pressure of arterial carbon dioxide

 FiO_2 = Fraction of air inspired that is oxygen

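### The SF-ratio model pools on-ventilator and post-extubation readings into one constant arm effect, so its result does not answer the SAP's stated question of change to the end of MV

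*SAP*

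**What the plan says.** SAP 17.4.4 introduces VI, OI, OSI and SF together and says the outcome will assess "evidence of a difference between arms in the change over time from baseline to the end of MV for the following measures". It then treats SF differently from the other three: "SF ratio will be reported at the above times while on MV but will also continue post MV", at every routine peripheral oxygen measurement and "at least twice in a 24-hour period". Protocol 8.4.2 agrees: "After extubation, all inhaled Oxygen and peripheral oxygen saturation parameters recorded as part of standard care must be transcribed into the CRF". No stopping point for SF readings is given in either place.

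SAP 17.4.4.2 specifies the SF model. "The dependent variable will be post baseline (0 hours) SF ratio measurements", with no restriction to time on MV. "Covariates will be: SF ratio at baseline (0 hours), treatment arm, time (fitted as a continuous variable"), and the prior-ventilation stratum; centre is a random intercept. One estimated mean difference is reported, with its CI and p-value. For VI, OI and OSI the same section uses joint modelling, because extubation cuts those series short in a possibly informative way. Its by-timepoint table and mean profile plots also cover only those three.

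Two other places bear on the question. SAP 9.2 limits VI, OI and OSI to time on MV but lists SF as a separate item without that limit. Protocol 11.5 puts SF in the joint modelling with the other three.

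**The concern.** A single arm coefficient with a common straight line in time estimates the average arm gap over whichever readings happen to exist. Those readings come from two different states: ventilated and extubated. Two consequences follow.

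- If SF is typically higher after extubation, the arm that comes off the ventilator sooner contributes higher readings at a given time since randomisation. The arm term can then be non-zero even when SF on the ventilator is identical.
- If surfactant raises SF on the ventilator only, the post-extubation readings, where the arms do not differ, pull the estimate towards zero.

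SF is one of the physiological outcomes meant to show whether surfactant improves gas exchange. A significant SF result could partly restate the primary outcome. A real on-ventilator gain could be reported as small or absent. No planned table or plot of SF would show which had happened.

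**Working it through.** **Plan's own figures.** The documents give no effect size, SD or power for SF. The MV-duration inputs come from Protocol 11.3 and reproduce:

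- Log-scale variance = ln(1 + CV²): ln(1 + 0.518²) = 0.237 and ln(1 + 0.613²) = 0.319.
- Log-scale difference = ln(4.08/4.83) − (0.319 − 0.237)/2 = −0.169 − 0.041 = −0.209 (unrounded inputs).
- n per group = (1.960 + 1.282)² × 0.556 / 0.209² = 133.2, so 134 for 90% power. For 80% power it is 99.5, so 100. 134/0.95 gives 142 per group, 284 in total.

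**Simulation A.** 142 per arm, 14 sites, log-normal MV durations as above, 300 trials per cell. On-MV readings are at 6, 12, 24, 36 and 48 h, then daily. (After 48 h, SAP 17.4.4 says every 48 h, while SAP 17.4.4.2 and the protocol say daily; daily was used.) Assumed, not in the documents:

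- post-MV readings 2/day for 3 days, 4/day for 4 days or 8/day for 5 days;
- between-infant SD 50, within-infant SD 40, drift +10 per day;
- SF step at extubation of 0, 60 or 120 units;
- correlation of infant SF level with MV duration 0 or 0.4 (the 0.4 runs were not completed for every schedule).

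The SAP model was given a participant intercept, which its text does not name, so these figures do not reflect that separate matter.

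MV shortened as planned, no on-MV SF effect, rejection at two-sided 0.05:

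| Analysis | Step 0 | Step 60 | Step 120 |
|---|---|---|---|
| All readings, as planned | 4-8% | 13-18% | 36-51% |
| On-MV readings only | 4-8% | 4-8% | 4-8% |

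With neither effect present, the all-readings model rejected 3-13%, the upper end at step 120. Only the excess over that is due to MV duration.

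On-MV SF effect of 20 units, no change in MV duration. The simple expectation is 20 × (1 − post-MV share):

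| Post-MV share of readings | Expected | Estimated | Power, all readings | Power, on-MV only |
|---|---|---|---|---|
| 43% | 11.4 | 12 | 57-71% | 97-99% |
| 68% | 6.4 | 7 | 29-35% | 97-99% |
| 84% | 3.2 | 3-4 | 12-17% | 97-99% |

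With both effects present, the all-readings estimate ran from 3.5 to 19.9 and rejection from 14% to 96%. Monte Carlo error is up to about ±6 points.

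**Simulation B.** 134 per arm, infant-clustered standard errors, 300 runs, 2-6 post-MV readings per day over 3-5 days. Assumed: SF about 220 rising by about 100 on MV, about 400 after extubation, SDs 45 and 35.

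- MV ratio 0.845, no on-MV SF effect: 50-62% rejection, against 6-8% on MV readings only. With ratio 0.92 the planned model rejects 16-25%.
- SF gain of 15 units over the first 48 h only: power 8-19%, against 73-74% on MV readings only.
- Both effects: 86-95% rejection.

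**Dependence on the post-extubation level.** A further 200-run check used ratio 0.845, no on-MV effect and 4 post-MV readings per day for 4 days. A common post-extubation SF of 400, 360 or 320 gave 58%, 39% or 23% rejection. A step of 0, 40 or 80 from each infant's own last level gave 6%, 9% or 25%.

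**Scale of a step, for illustration.** SF = SpO2/FiO2. At SpO2 95%, SF is 95/0.40 = 238, 95/0.30 = 317 and 95/0.21 = 452. The SpO2 and the first two FiO2 values are assumed; 0.21 is room air.

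**The case against.** The strongest reply is that SF after MV is intended. SAP 9.2 and Protocol 3.6.2 attach the on-ventilator limit to VI, OI and OSI. A Protocol 3.6.2 footnote values SF because it remains available once MV has stopped, and Protocol 8.4.2 requires post-extubation readings. If the target is SF over the whole recorded stay, higher SF from earlier extubation is a genuine treatment effect and rejection is not false. This stands in part: the on-MV null is not the only possible reading, and a reader should not infer that collecting or reporting post-MV SF is an error. It does not rescue the model. SAP 17.4.4 says end of MV, Protocol 3.6.2 speaks of change over time, and a constant arm effect weighted by how often nurses record saturation expresses neither.

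Second, OSI = MAP × FiO2 × 100 / SpO2 = 100 × MAP / SF. OSI is confined to MV and jointly modelled, so an on-MV gain could be seen there. This also stands in part: OSI moves with MAP too, so it is not a substitute for SF.

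Third, the size depends on an SF step that the documents do not give. SAP 17.4.5 and 17.4.7 anticipate oxygen and non-invasive support after extubation, which could keep the step small. This stands, and the claim is conditional on it.

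Fourth, the trial expects better gas exchange to lead to shorter MV (Protocol 3.4.1), so both effects may occur and the model may well reject. That is so, but the result could not then be attributed to oxygenation on the ventilator.

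**Conclusion.** The point holds in conditional form. The SF analysis does not match the question in SAP 17.4.4, and its single mean difference mixes two periods. With MV shortened as planned and no on-MV SF effect, rejection runs from about 5% (no step at extubation) to about 50-60% (a large step). An on-MV effect shrinks roughly by the share of readings taken after MV. The size of the step, the SDs and the number and duration of post-MV readings are all assumptions.

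A reader might infer that the model will reject whenever MV duration differs, or that it will miss any real oxygenation effect. The documents support neither. The first needs an SF step of unstated size, and the second is dilution, with power between 12% and 71% in simulation A. Nor should 50-62% be read as the false-positive rate: it is the top of the range and comes from an assumed post-extubation SF of about 400.

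The departure from Protocol 11.5 is not proof of an unplanned change. The SAP declares compliance with protocol v3.0 and its change log cites v6.0, while the amendment log of the protocol supplied ends at v2.0.

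This concerns one secondary outcome. The primary result is unaffected.

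**What to change.** 1. In SAP 17.4.4, state one SF estimand and reconcile it with SAP 9.2: change on MV, SF over a defined stay, or both named separately. If post-MV SF is kept, give the point at which readings stop.
2. In SAP 17.4.4.2, analyse on-MV SF in the same joint model as VI, OI and OSI, as Protocol 11.5 states, and add SF to the by-timepoint table and profile plots.
3. Report post-extubation SF separately.
4. At minimum, if one mixed model is kept, add treatment-by-period (on MV / after MV) and treatment-by-time terms and report each period's effect with its CI.

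Simply restricting an ordinary mixed model to MV readings would remove the mixing but drop the handling of informative drop-out that the SAP considers necessary for VI, OI and OSI. Item 4 has the same limit, so the joint model is preferable. A contrast over a fixed early window such as 6-48 h is optional; no section names it as the SF target.

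The data are already collected. The cost is SAP wording, a little extra programming, and two SF results to report instead of one.

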11.5 Analysis Plan

A full SAP will be written prior to the conduct of any comparative analysis of the treatment arms. The main features of the SAP are included here.

The primary analysis will be a test of the difference in geometric mean durations of MV between groups (placebo vs. poractant alfa), reported with the corresponding 95% confidence interval. The analysis will be conducted according to the intent-to-treat principle, and will incorporate the stratification factors of duration of ventilation (<24hrs and >=24hrs) prior to randomisation and site.

For the secondary outcomes, longitudinal data for VI, OI, OSI and SF will be analysed with joint modelling. LRSQ data will be modelled longitudinally and comparisons made between groups. Binary data will be reported in terms of relative risk with 95% confidence intervals.

Within BESS, data will be collected as to ascertain readiness for spontaneous breathing test and time of extubation.

As much information as possible will be collected about the reasons for missing outcome data; this will be used to inform any imputation approaches employed in the analysis. Such methods will be fully described in the SAP.

IRAS 220853 Page **63** of **87**

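### The SAP's SF-ratio model names centre as its only random effect and specifies nothing for the infant; fitted as listed, its confidence interval and p-value would be anti-conservative.

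*SAP*

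**What the plan says.** SAP 17.4.4.2 introduces the analysis this way: "For the SF ratio, a repeated measures random effects model will be fitted". On the response it says "The dependent variable will be post baseline (0 hours) SF ratio measurements", so each infant contributes several rows. The fixed terms are baseline SF, treatment arm, time as a continuous variable and the prior-ventilation stratum (under 24 h, or 24 h and over). The one random term is given by "Centre will be fitted as a random intercept". On reporting it says "The treatment effect (estimated mean difference in SF ratio) will be reported together with a 95% CI and a p-value".

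SAP 17.4.4 sets the reading schedule. After the pre-intervention sample, readings are taken "at 6, 12, 24, 36 and 48hrs while still on MV and will continue every 48hrs if still on MV". For SF they continue after extubation whenever saturation is charted, and "at least twice in a 24-hour period". Protocol 8.4.2 likewise asks for all post-extubation oxygen and saturation values from standard care to be transcribed.

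Neither document states an infant-level random effect, a within-infant residual covariance, a subject identifier or a robust standard error for this model. SAP section 5 names SAS for everything except the joint models.

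**The concern.** Arm is constant within an infant, so the information about the treatment effect lies mainly between infants. A centre intercept absorbs what infants in one unit share. It does not absorb what one infant's readings share. If nothing else is fitted, ten readings on one infant count almost as ten infants, and the interval and p-value are too tight.

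The same centre-only random structure appears in the SAP's mixed models for the primary outcome (17.4.1.2) and the respiratory questionnaire (17.4.9.2). It is adequate there because each infant gives one row. It does not carry over to SF, where each infant gives many.

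At stake is a false claim of a difference on a secondary efficacy outcome that will be reported with a p-value and, under SAP section 12, without multiplicity adjustment. SAP section 21 limits independent programming to the primary and safety analyses, so that check would not catch a literal fit of this model.

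**Working it through.** **The plan's own figure.** The documents give no power or error rate for SF. The related figure is the trial size in protocol 11.3. With κ₁ = 2.5/4.83 = 0.518, κ₂ = 2.5/4.08 = 0.613 and δ = 4.08/4.83 = 0.845, the log-normal formula is

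n = (z_α/2 + z_β)² [ln(1+κ₁²) + ln(1+κ₂²)] / [ln δ − ½(ln(1+κ₂²) − ln(1+κ₁²))]²

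It gives 99.5, rounded up to 100 per group (80% power), and 133.2, rounded up to 134 (90% power). Then 134/0.95 = 141.05, rounded up to 142 per group, or 284 in total. All of these reproduce, and 284 is used below.

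**Readings per infant (m).**
- Mean ventilation of 4.83 days (protocol 11.3) is 115.9 h. That gives five readings up to 48 h.
- After 48 h, SAP 17.4.4 says every 48 h, while the summary table in 17.4.4.2 uses every 24 h. This adds one reading (96 h) or two (72 and 96 h).
- Mean PICU stay is 6.1 days (protocol 3.2), and 6.1 − 4.83 = 1.27 days. At the floor of two a day this adds about three readings.
- The total is about 9 or 10. Charting more often would raise it. I show 5, 10 and 20.

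**Within-infant correlation (ρ).** The documents give none. The relevant value is what remains after adjusting for baseline SF. I show 0.1, 0.3 and 0.5 as assumptions.

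**Formula, constant correlation.** The design effect is DE = 1 + (m − 1)ρ. The standard error is too small by a factor of √DE. The true two-sided error of a nominal 5% test is 2[1 − Φ(1.96/√DE)].

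| m | ρ = 0.1 | ρ = 0.3 | ρ = 0.5 |
|---|---|---|---|
| 5 | DE 1.4, 9.8% | DE 2.2, 18.6% | DE 3.0, 25.8% |
| 10 | DE 1.9, 15.5% | DE 3.7, 30.8% | DE 5.5, 40.3% |
| 20 | DE 2.9, 25.0% | DE 6.7, 44.9% | DE 10.5, 54.5% |

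For example, with m = 10 and ρ = 0.3, √3.7 = 1.92 and 1.96/1.92 = 1.02, so the two-sided tail is 30.8%.

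**Formula, decaying correlation.** If readings k steps apart correlate at ρᵏ, then DE = 1 + 2Σ(1 − k/m)ρᵏ for k = 1 to m − 1. With m = 10, DE is 1.735, 2.600 and 4.155 for adjacent-reading correlations of 0.3, 0.5 and 0.7. The true errors are 13.7%, 22.4% and 33.6%.

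**Simulation under no treatment effect.** The set-up was 284 infants, 14 centres, log-normal ventilation times with mean 4.83 and SD 2.5 days, the SAP schedule with 24-hourly readings after 48 h, three post-extubation readings (average 10.3 per infant) and 1,000 runs per ρ. Centre was entered as fixed effects for speed. The infant term was fitted using the true ρ.

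| ρ | Type I error, centre only | Reported SE / true SD | Type I error, infant intercept added |
|---|---|---|---|
| 0 | 0.046 | 1.03 | 0.046 |
| 0.1 | 0.172 | 0.71 | 0.055 |
| 0.3 | 0.327 | 0.49 | 0.054 |
| 0.5 | 0.430 | 0.41 | 0.049 |

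At each non-zero ρ, the centre-only error is slightly above the closed form for m = 10; the simulated infants have unequal numbers of readings. Adding the infant intercept brings the error back to about 5%.

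**The case against.** The best reply is the label. The SAP calls this a repeated-measures model. In SAS, a residual covariance with infant as subject can sit alongside a random centre intercept; that would fit every word of the section and handle the correlation without an infant random effect. This stands as far as it goes. A reader might infer that the SAP commits to treating readings as independent and that the p-value will certainly be too small. The documents do not support that, because the SAP never says so. But a label compatible with a correct model does not specify one, and the only random effect written down is centre.

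The size is also assumed rather than known. At low or decaying correlation the inflation is smaller, which is why the range is shown. It remains material at the low end: about 10% with 5 readings at a constant 0.1.

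Four further inferences are tempting and not supported:
- **A better model was abandoned.** The supplied protocol (11.5) says "longitudinal data for VI, OI, OSI and SF will be analysed with joint modelling", and the SAP keeps that for VI, OI and OSI only. However, the SAP justifies joint modelling by measurement ending at extubation, and SF continues afterwards. The SAP also refers to protocol versions 3.0 and 6.0, while the supplied protocol's history ends at 2.0. The difference does not show a lapse.
- **SF would carry the mechanistic argument.** The protocol lists SF as a secondary efficacy outcome. Mechanism belongs to Work Package C, which does not inform trial outcomes.
- **Sicker infants carry more weight.** Nothing quantifies this. Under SAP 17.4.4, an infant ventilated beyond 48 h is read every 48 h, while an extubated infant is read at least twice a day.
- **A random slope or treatment-by-time term is also required.** These are modelling preferences. The SAP's stated effect is a baseline-adjusted mean difference, and the infant intercept alone restored the error rate in the simulation, which had no infant-specific slopes.

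**Conclusion.** The point holds as an under-specified model. Followed literally, SAP 17.4.4.2 gives an interval and p-value for SF that are too optimistic. At 10 readings per infant and constant residual correlations of 0.1, 0.3 and 0.5, the 5% test has a true error of about 16%, 31% and 40%, with standard errors too small by factors of 1.38, 1.92 and 2.35. Across 5 to 20 readings the range is 9.8% to 54.5%. With decaying correlation it is about 14% to 34% at 10 readings.

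These figures rest on assumed correlations, on reading counts inferred from mean stays, and on the model being fitted with nothing for the infant. If the statistician already intends a within-infant covariance, the error does not arise and only the text needs completing. The primary analysis and the sample size are not affected. It should be settled before the randomisation codes are released.

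**What to change.** Add one sentence to SAP 17.4.4.2 naming the infant as the unit on which readings repeat. Either of these would do:
- a random intercept for infant nested in centre; or
- a stated residual covariance with infant as subject, for example spatial power, which suits unequally spaced times.

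Keep the centre random intercept and the listed covariates. The reported quantity stays the baseline-adjusted mean difference.

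The cost is one sentence in the SAP and one statement in the model code. It needs no new data and no change to the sample size. While the section is open, reconcile the reading interval after 48 h between 17.4.4 and the summary table in 17.4.4.2.
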